Alyatec has performed a validation study in the EEU, evaluating 20 patients with cat allergy (by history, positive skin prick test, and positive IgE) and mild asthma, defined by the Global Initiative for Asthma stage 1 (GINA 1: asthma symptoms are controlled with short-acting beta agonists as needed, asthma symptoms are rare, there is no night awakening due to asthma, no exacerbations in the last year, and normal FEV1) (Bateman, 2008), as well as 10 patients with GINA 1 asthma and other allergies, but not cat allergy (by history, negative skin prick test to cat, and negative IgE to cat hair, and positive skin prick test and IgE to other allergens, eg, mite, grass, birch, or ash). All 30 patients were exposed continuously to nebulized cat allergen (40 ng/m^3 Fel d 1) in the EEU for a maximum of 2 hours. Patients underwent spirometry with FEV1 testing every 10 minutes during the EEU exposure and were removed from the EEU when they experienced bronchoconstriction, when their FEV1 was reduced by  $\geq 20\%$ , defined as an EAR. Patients were then monitored outside of the EEU for 6 hours to assess if/when a late asthmatic response (LAR) occurred, defined as a delayed drop of 15% after exiting the allergen exposure in the EEU. Fifty percent (50%) of patients achieved an EAR within 2 hours of EEU exposure and of those who achieved an EAR, approximately 50% of those achieved a LAR. The mean reduction in FEV1 during EAR and LAR was -28.1% range (-20.2 to -44.6) and -19.5% range (-14.9 to -23.5) respectively. Patients experienced EARs as early as within 30 minutes of exposure in the EEU to as late as 121 minutes; the mean time to an EAR was 60 minutes and the mean time to a LAR was 180 minutes (Radu, 2018) (Gherasim, 2018). None of the non-cat-allergic asthmatic patients reached EAR and only experienced minimal changes in FEV1 during cat allergen exposure, with a mean change of FEV1 of 2%, suggesting that the cat-allergen exposure unit is highly specific. All patients tolerated the allergen exposure well. Cat-allergic asthmatic patients who experienced an EAR were offered treatment with a short-acting  $\beta$ 2 agonist upon exiting the EEU chamber, and those who experienced a LAR were also treated with a short-acting  $\beta$ 2 agonist, with all patients experiencing a return of FEV1  $\geq 90\%$  baseline after EAR and LAR. None of the 20 cat-allergic patients with asthma required escalation of asthma therapy beyond a short-acting  $\beta$ 2 agonist, demonstrating that the FEV1 changes induced by the allergen exposure in the EEU are reversible and highly responsive to therapy.

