the EEU for 6 hours for safety follow-up, during which time the LAR is measured if it occurs. During this 6-hour observation period, spirometry will be performed every 30 minutes, and TNSS, TOSS, and chest symptom questions are recorded every hour. At the end of 6-hour monitoring period, patients will be discharged home if their FEV1 is  $\geq 90\%$  of the baseline value; additional monitoring will be performed if the FEV1 is below 90%. A physical examination and vital signs measurement will also be performed prior to leaving the clinical trial unit. FEV1 will be monitored at home using a portable hand-held spirometer for approximately 18 hours after leaving the clinical unit (a total of 24 hours of monitoring from the end of the EEU exposure). Alyatec's investigator(s) will be connected to spirometry data performed by the patients at home. If there is a 30% drop in FEV1, the investigator(s) will receive an alarm by email to inform him/her about the change in spirometry and the patient will be contacted and evaluated by a medical doctor. Patients will also receive contact information that they will be able to contact Investigator(s) 24 hours a day in case of symptoms.

Cat-allergic patients who fail to reach EAR within 2 hours during baseline exposure will be excluded from the study. At time point days 8, 29, 57, and 85 after randomization, patients will be exposed to the EEU for a maximum of 4 hours or until they reach EAR (FEV1 reduction  $\geq 20\%$ ) and then will be monitored outside of the EEU for 6 hours for safety follow-up, during which time the LAR is measured if it occurs. Although the amount of Fel d 1 that is nebulized into the EEU is continuously  $40 \text{ ng}/\text{m}^3$ , the individual exposure increases over time in association with minute ventilation (the volume of air that can be inhaled or exhaled for 1 minute). Therefore, minute ventilation will be measured in each patient at baseline using spirometry, so that the Fel d 1 airborne exposure, as a product of the individual's minute ventilation and time, can be assessed at each Cat Allergen Challenge on days 8, 29, 57, and 85. Minute ventilation will be measured 1 time at baseline while the patient is at rest rather than in real time in the EEU during cat allergen exposure to minimize variability in the measurement.

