#### **6.2.1. Inclusion Criteria**

A patient must meet the following criteria to be eligible for inclusion in the study:

1. Generally healthy men and women between the ages of 18 and 65 inclusive at the time of screening.
2. Documented or patient reported history (for at least 2 years) of symptomatic cat allergen-triggered asthma with rhinitis with or without conjunctivitis as defined by all of the following criteria:
  - a. Positive skin prick test (SPT) with cat hair extract (mean wheal diameter at least 5 mm greater than a negative control) at screening
  - b. Positive allergen-specific IgE (sIgE) tests for cat hair and Fel d 1 (>0.35 kAU/l at screening)
  - c. History of asthma GINA 1
  - d. Screening FEV1  $\geq$ 70% predicted after withholding long-acting  $\beta$ 2-agonists for > 36 hours and short-acting  $\beta$ 2-agonists for > 6 hours
  - e. Demonstrated  $\geq$ 20% fall in FEV1 within 2 hours during Cat Allergen Challenge in EEU and ability to withstand exposure for at least 10 minutes during screening
3. Willing and able to comply with clinic visits and study-related procedures
4. Provide informed consent signed by study patient or legally acceptable representative

5. Patients covered by health social identification number
6. Able to understand and complete study-related questionnaires
7. No cat exposure at home for the past year and must continue having no exposure at home during the study; cat exposure outside of the home shall be avoided for at least 1 week prior to any Cat Allergen Challenge and during the defined follow-up period.
8. Less than 10 pack-years of smoking history

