5.6.1. Analysis of Primary Efficacy Variable(s)

The time to EAR for each treatment will be examined using Kaplan Meier estimates with patients being censored at 4 hours if they did not experience an EAR and remained in the EEU for 4 hours. If a patient leaves the EEU before experiencing an EAR and for reasons unrelated to their clinical symptoms, they will be censored at the time of EEU departure. The median time to EAR for each treatment group and the corresponding 95% confidence intervals will be presented for each Controlled Cat Allergen Challenge. A formal comparison of time to EAR in the treatment groups at day 8 will be performed using a Cox proportional hazards model, adjusting for allergen concentration in the EEU and time to EAR in the baseline Cat Allergen Challenge. In patients who receive EEU related medications (including medications given on-site and rescue medications taken at-home), the impact of the carryover of medications between challenges will be explored by including taking medication or not as baseline variable for the model of each subsequent visit. A one-sided 5% statistical test of the hazard ratio for placebo compared to drug will be performed.

If the Cox proportional hazards model does not converge, an extension of the Wilcoxon Rank Sum test comparing the ranks of time to EAR under censoring, adjusted by the covariates specified above, will be used ([LaVange and Koch, 2006](#)). As an additional sensitivity analysis, the presence or absence of an EAR within the 4-hour period in the REGN1908-1909 treatment group as compared to placebo will be tested using a Fisher's Exact Test.

Subgroup analyses may be performed by gender, age, baseline IgE and the ratio of Fel d 1 IgE to Cat Allergen IgE at baseline. The ratio of Fel d 1 IgE to Cat Allergen IgE at baseline (log transformed if the distribution is skewed) will also be explored as potential covariate in the Cox proportional hazards model.

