5.6.3. Analysis of Other Efficacy Variables

The time to LAR at each of the Controlled Cat Allergen Challenges in an EEU will also be explored. After the allergen challenge (when the patient exits the EEU), the patient is observed

onsite for 6 hours and then for an additional 18 hours at home. If a patient does not experience an LAR within the 24-hour period, their time to LAR will be censored at 24 hours.

The time to LAR will be defined as the time to a $\geq 15\%$ reduction in FEV1 during the 6-hour onsite observation period (adjudicated by the blinded investigators). During the at-home monitoring period up to 24 hours after the patient exits the EEU, the time to LAR will be defined as the time to a $\geq 15\%$ reduction in FEV1 (confirmed by two spirometry efforts within 5 minutes) along with either rescue medication use (any medication at any dose) within 1 hour or the presence of chest symptoms within 1 hour of the drop in FEV1 (adjudicated by the blinded investigators). Chest symptoms are identified by a response of Mild, Moderate or Severe to the chest symptom questions involving chest tightness, wheezing, cough, throat tightness, and difficulty breathing. Multiple asthma exacerbations during the observation period or at-home monitoring period within the same patient may be adjudicated by the site to be an extended LAR (no more than one LAR within 24 hours of leaving the EEU may be adjudicated, e.g. a subject cannot have more than one LAR within 24 hours of leaving the EEU).

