The time to LAR for each treatment will be examined using Kaplan Meier estimates with patients being censored at 24 hours if they did not experience an LAR. The median time to LAR for each treatment group and the corresponding 95% confidence intervals will be presented for each Controlled Cat Allergen Challenge. A formal comparison of time to LAR in the treatment groups at each EEU challenge visit will be performed using a Cox proportional hazards model, adjusting for allergen concentration in the EEU. The Kaplan Meier and Cox Proportional Hazards models will be fit separately on the subgroup of patients who receive rescue medications upon EEU exit and for patients who do not. In patients who receive EEU related medications (including medications given on-site and rescue medications taken at-home), the impact of the carryover of medications between challenges will be explored by including taking medication or not as baseline variable for the model of each subsequent visits. A one-sided statistical test of the hazard ratio for placebo compared to drug will be performed.

The ratio of Fel d 1 IgE to Cat Allergen IgE at baseline will also be explored as potential covariate in the Cox Proportional Hazards model and will be log transformed if necessary.

If the Cox proportional hazards model does not converge, an extended Wilcoxon Rank Sum test comparing the ranks of time to LAR, adjusted by the covariates specified above, will be used ([LaVange and Koch, 2006](#)).

A time-to-event analysis with competing risks may also be used to examine the incidence of LAR, where the use of rescue medications upon EEU exit is treated as a competing risk with allergen concentration as a covariate in the model. The comparison of LAR-specific and rescue medication-specific cumulative incidences within 24 hours of an EEU challenge across treatment groups will be performed using Gray's method. The model will be fit for each EEU Challenge visit.

As an additional sensitivity analysis, the presence or absence of an LAR within the 24-hour period in the REGN1908-1909 treatment group as compared to placebo will be tested using a Fisher's Exact Test.

The time course of asthma response comprising both EAR and LAR will also be visualized and summarized. A similar analysis will be repeated for the time to any Asthma Reaction. The first asthma reaction that occurs, whether it occurs while the patient is in the EEU, in the on-site 6-

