hour observation period, or in the at-home monitoring period, will be treated as the event time. If the subject experiences no asthmatic reaction at a given Allergen Challenge visit, the patient's time will be censored at 24 hours. Kaplan-Meier estimates and curves will be produced for each visit.

The presence or absence of any asthma exacerbation (EAR or LAR) in the REGN1908-1909 treatment group as compared to placebo will be tested using a Fisher's Exact Test.

Individual spaghetti plots and mean plots of the percent change in FEV1 over time will also be examined. LOCF will be used in the calculation for any graphical displays of the mean change in FEV1 over the Cat Allergen Challenge.

The peak TNSS and TOSS and change from pre-challenge baseline to peak TNSS and TOSS across EEU challenge visits may also be examined using MMRM models.

The change and percent change from the Baseline Cat Allergen Challenge in the Fractional exhaled Nitric Oxide (FeNO) (adjusted for the pre-challenge baseline) will be explored using an MMRM model, with the treatment, visit, and treatment by visit interaction, and use of steroid rescue medications within 24 hours of the EEU challenge as factors. The time in EEU will be included as a covariate in the model.

The skin prick test with serial allergen titration with cat allergen will also be compared between treatment groups using an MMRM model, with the treatment, visit and treatment by visit interaction as factors.

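### Two exploratory models omit a baseline value the trial already collects: LAR at the baseline challenge in the time-to-LAR model, and the visit 3 wheal AUC as a covariate in the titrated skin-test model

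*SAP*

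**What the plan says.** **Entry.** Protocol 6.2.1, criterion 2e, requires a 20% or greater "fall in FEV1 within 2 hours during Cat Allergen Challenge in EEU". No entry criterion mentions LAR.

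**How common LAR is.** Protocol section 1 reports from the site's validation study that, "of those who achieved an EAR, approximately 50% of those achieved a LAR". Observation in that study lasted 6 hours.

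**What is measured at baseline.** After the baseline challenge patients are observed for 6 hours, "during which time the LAR is measured if it occurs" (Protocol section 1). Footnotes 5 and 6 of the schedule of events give visit 3 the same on-site and home spirometry and symptom questions as the later challenges, and a rescue kit is handed out at that visit too. The LAR definition in SAP 5.6.3 can therefore be applied to visit 3.

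**The LAR models.** The comparison at each challenge is "performed using a Cox proportional hazards model, adjusting for allergen concentration in the EEU" (SAP 5.6.3). Medication carry-over is an exploratory addition, and so is an IgE ratio: "The ratio of Fel d 1 IgE to Cat Allergen IgE at baseline will also be explored as potential covariate". Fits are also split by rescue use at exit from the exposure unit. For patients without an event, "their time to LAR will be censored at 24 hours". The rank-test fallback takes the same covariates, and the competing-risk model takes allergen concentration only. Baseline-challenge LAR appears in none of them.

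**The comparison models.** The primary EAR model is fitted "adjusting for allergen concentration in the EEU and time to EAR in the baseline Cat Allergen Challenge" (SAP 5.6.1). The secondary models in SAP 5.6.2 adjust for baseline-challenge AUC or baseline tolerated allergen quantity, even though their outcomes are already changes from baseline.

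**Titrated skin test.** SAP 4.5.3 defines the variable as change and percent change in wheal AUC from baseline. SAP 5.6.3 analyses it "using an MMRM model, with the treatment, visit and treatment by visit interaction as factors", with no baseline covariate.

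**The concern.** The SAP adjusts its primary and secondary efficacy models for the patient's own response at the baseline challenge. The LAR and skin-test models depart from this, and no reason is given.

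For LAR the omission could matter. Every randomised patient is an early responder, but the trial may mix patients prone to a late response with patients who are not. If the tendency is stable within a patient, baseline LAR explains much of the variation. A Cox model without it then has less power and estimates a hazard ratio nearer 1 than the one comparing like patients.

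For the skin test the issue is precision alone.

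At stake is the reading of an exploratory objective in a proof-of-concept trial of about 60 patients, with a formal one-sided LAR comparison planned at each challenge. No primary or secondary conclusion depends on it.

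**Working it through.** **1. The plan's own power figure.** The plan states no power for LAR or the skin test. Its 84% for time to EAR (SAP 2.2) was reproduced first, to confirm the sample-size reading.
- 30 per arm less 8 dropouts in total leaves 26 per arm.
- With exponential times, medians of 58 and 132 minutes and censoring at 240 minutes, event probabilities are 1 − exp(−ln2 × 240/58) = 0.943 and 1 − exp(−ln2 × 240/132) = 0.716.
- Events: 26 × (0.943 + 0.716) = 43.1 (43.2 with unrounded inputs).
- Schoenfeld power, one-sided 5%: Φ(√(43.2/4) × |ln 0.44| − 1.645) = Φ(1.05) = 85.4%. At a hazard ratio of 1/2.25 it is 84.6%.

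The stated figure is reproduced, so 26 per arm and a hazard ratio of 0.44 are carried forward.

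**2. LAR: assumptions.** From the documents: half of patients with baseline LAR, 24-hour censoring, a one-sided test. Assumed: alpha 5% as for the primary, a 50% placebo LAR risk, a true hazard ratio of 0.44 borrowed from EAR, exponential times, and a hazard ratio of 1, 2, 4 or 8 for baseline LAR yes against no.

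To see what those ratios mean, let x be the 24-hour LAR-free probability on placebo without baseline LAR. An overall risk of 50% with equal halves requires x + x^HR = 1:
- HR 2: x = 0.618, so risks are 62% with and 38% without baseline LAR.
- HR 4: x = 0.724, so 72% and 28%.
- HR 8: x = 0.812, so 81% and 19%.

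**3. LAR: results** (2,500 simulated trials per row, about 20 events each; the last column is from one very large simulated sample).

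| Baseline-LAR HR | Power without | Power with | Loss (points) | Unadjusted HR, large sample |
|---|---|---|---|---|
| 1 | 54.6% | 54.6% | 0 | 0.44 |
| 2 | 53.6% | 55.4% | 1.8 | 0.44 |
| 4 | 48.3% | 54.8% | 6.5 | 0.48 |
| 8 | 42.6% | 56.4% | 13.8 | 0.51 |

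With a 35% placebo risk, power goes from 38.6% to 39.8% (HR 2) and from 37.9% to 42.0% (HR 4).

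Under no treatment effect, one-sided type I error was 5.0 to 5.4% without the covariate and 5.2 to 6.1% with it, so the gains are slightly flattered.

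**4. LAR: sparse events.** At a baseline-LAR HR of 8, the chance that a given patient is in the no-baseline-LAR half and has an event is 0.5 × 0.188 = 0.094 on placebo and 0.5 × (1 − 0.812^0.44) = 0.044 on drug. The chance that this half has no event at all is (0.906 × 0.956)^26, about 2.4%. In those trials the covariate estimate diverges.

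**5. Skin test.** With correlation r between baseline and follow-up and equal variances, a change score has variance proportional to 2(1 − r), and the baseline-adjusted analysis 1 − r². The ratio is (1 + r)/2: 0.65, 0.75 and 0.85 at r = 0.3, 0.5 and 0.7, a reduction of 35%, 25% and 15%.

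Where the adjusted model has 80% power, the change score without the covariate has Φ(2.487 × √((1 + r)/2) − 1.645) = 64%, 69% and 74%. Here 2.487 is 1.645 + 0.842. The values of r are assumptions. The algebra is for the change score; percent change is not covered exactly.

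**The case against.** The case for leaving the plan alone is respectable.

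- Both endpoints are exploratory, no power is claimed for them, and nothing confirmatory depends on them. This stands.
- The unadjusted LAR test is valid, and its error rate already covers chance imbalance. The unadjusted hazard ratio is a legitimate marginal quantity; its distance from the adjusted one is non-collapsibility, not an error. This stands.
- The documents give no within-patient repeatability of LAR. The 50% rests on about 10 early responders (20 cat-allergic patients × 50%) watched for 6 hours, whereas the SAP window is 24 hours. The baseline challenge lasts at most 2 hours and ends with a bronchodilator; later ones last up to 4 hours. Baseline LAR may predict weakly, so the range has to start at zero.
- With about 20 events, and splits by rescue use, another covariate is not entirely free. This also stands, and the fix has to deal with it.

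A reader might infer three stronger things that the documents do not support:
- *The skin-test analysis ignores baseline and shrinks the effect.* SAP 4.5.3 makes the outcome a change from baseline, and under randomisation a linear model without the covariate is less precise but not attenuated.
- *The LAR analysis is seriously underpowered by this choice.* That needs very strong prognosis. Placebo risks of 0.9 and 0.1, for example, imply a baseline-LAR hazard ratio of ln 0.1 / ln 0.9 = 21.9, for which the documents give no basis and at which sparse events are most troublesome.
- *The late response is a main claim of the trial.* The Protocol lists it among the exploratory objectives.

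None of this is a reason to keep the covariates out. If baseline LAR is not prognostic, power is the same with and without it (54.6%).

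**Conclusion.** The point holds as a near-free improvement to two exploratory analyses, not as a flaw that invalidates either.

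For LAR, the benefit runs from nothing to about 14 power points, and the estimated hazard ratio moves from 0.44 to at most about 0.51, over the assumed baseline-LAR hazard ratios of 1 to 8. At 2 the gain is negligible; it becomes worth having at about 4. Where the trial sits in that range cannot be settled from the documents. The figures also depend on the assumed placebo risk and treatment effect.

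For the skin test, the gain is precision only, and its size depends on the assumed correlation.

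The reason to act is consistency with SAP 5.6.1 and 5.6.2, together with a favourable balance: a possible gain against a very small cost.

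**What to change.** Amend SAP 5.6.3 before anyone is unblinded, which means before the first-step analysis if that is performed.

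1. Add LAR at the visit 3 challenge (yes/no, by the same adjudicated definition used after randomisation) as a covariate in the time-to-LAR Cox model, its rank-test fallback and the competing-risk model.
2. State in advance what is done if one baseline-LAR stratum has no events, for example Firth penalisation or stratification by baseline LAR. Also state how a patient whose visit 3 LAR status cannot be determined is handled.
3. Add the visit 3 titration AUC, with a baseline-by-visit term, as a continuous covariate in the skin-prick MMRM.

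**Cost.** SAP wording and adjudication of visit 3 LAR; no new data collection. The LAR covariate uses one degree of freedom, and the skin-test baseline and baseline-by-visit terms a few. The main downside is possible instability of the LAR model when events are sparse, which item 2 addresses.

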4.4.1. Rescue Medications

As soon as the patient has a drop in FEV1 of 20% and/or asthma symptoms, the patient will be removed from the EEU and will be treated with short-acting β 2 agonist every 20 minutes for 1 hour if necessary. Patients will stay under supervision in the observation room during 6 hours after leaving the EEU and FEV1 will be monitored every 30 minutes. During this 6-hour monitoring period, a LAR can appear with a drop in FEV1 of 15% and will be treated with short-acting β 2 agonist and corticosteroids if necessary.

After each allergen challenge, all patients will leave the site with a rescue treatment kit containing: short-acting β 2 agonist, oral corticosteroids, and oral antihistamines. The patients will also receive oral and written information about the procedure to be followed in case of the occurrence of AEs which may be related to the study, as well as the telephone number of the physicians of the study.

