4.5. Efficacy Variables

4.5.1. Primary Efficacy Variables

The primary endpoint in the study is the time to EAR upon Controlled Cat Allergen Challenge in an EEU on day 8. The time to EAR will be defined as the time to a $\geq 20\%$ reduction in FEV1 or when the patient voluntarily departs the EEU due to clinically significant allergic and/or asthma symptoms. During the allergen challenges (post-randomization), the patient may remain in the EEU for a maximum of 4 hours. If a patient does not experience an EAR and remains in the EEU for the maximum time, their time to EAR will be censored at 4 hours. Censoring implies that the time to EAR is at least 4 hours, but the exact time is unknown.

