4.5.3. Exploratory Efficacy Variables

The exploratory efficacy variables are:

- Time to Late Asthmatic Response (LAR) on days 8, 29, 57, and 85
- Time to Any Asthmatic Response on days 8, 29, 57, and 85
- Change and percent change from FeNO (parts per billion) (adjusted for the pre-challenge baseline) from baseline to days 30 and 86
- Change and percent change in the skin prick test with serial allergen titration, measured by AUC of the wheal sizes (diameter) over log-transformed allergen concentrations with cat allergen from baseline to day 29, 85, and 113

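### The optional competing-risk analysis of LAR estimates 'LAR without exit rescue', not the incidence of LAR; separately, the only FeNO model adjusts for two post-randomisation variables

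*SAP*

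**What the plan says.** SAP 4.5.3 lists "Time to Late Asthmatic Response (LAR) on days 8, 29, 57, and 85" among the exploratory variables. Under SAP 5.6.3 the window opens when the patient leaves the EEU: six hours on site, then home monitoring, described as "During the at-home monitoring period up to 24 hours after the patient exits the EEU".

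The main LAR analyses in that section are Kaplan-Meier estimates, a Cox model by treatment group, and a Fisher test of any LAR within 24 hours. The section then adds that a competing-risk analysis "may also be used to examine the incidence of LAR, where the use of rescue medications upon EEU exit is treated as a competing risk". Gray's method is then to compare "LAR-specific and rescue medication-specific cumulative incidences within 24 hours of an EEU challenge across treatment groups".

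On exit rescue, SAP 4.4.1 and Protocol 7.4 share one trigger: "As soon as the patient has a drop in FEV1 of 20% and/or asthma symptoms, the patient will be removed from the EEU", with a short-acting beta-2 agonist then given if needed. The EAR definition in SAP 4.5.1 is close to this: a 20% fall in FEV1, or "when the patient voluntarily departs the EEU due to clinically significant allergic and/or asthma symptoms". For the screening challenge, the Protocol Introduction and SAP 1.1 say without qualification that patients receive a short-acting beta-2 agonist on leaving the EEU.

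For FeNO, SAP 5.6.3 plans one mixed model. It has steroid rescue within 24 hours of the challenge as a factor and time in the EEU as a covariate.

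**The concern.** A competing event should occur during follow-up and prevent the event of interest, or at least end interest in it. Exit rescue does neither. It sits at the time origin, before any LAR can be observed. It is largely a consequence of the EAR, the outcome that the drug is meant to reduce. LAR remains possible afterwards: in the validation study, patients "who experienced an EAR were offered treatment with a short-acting" beta-2 agonist on leaving the chamber, and "of those who achieved an EAR, approximately 50% of those achieved a LAR". SAP 5.6.3 itself fits LAR models in the exit-rescued subgroup, so it treats LAR after rescue as observable in one paragraph and as excluded in another.

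The stake is interpretation. A curve presented as LAR incidence would leave out LARs in rescued patients, possibly most LARs, and could make a real LAR benefit look small or absent.

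The FeNO model raises a related but separate question. Time in the EEU is essentially the time-to-EAR outcome, and steroid rescue is also post-randomisation. Adjusting for them can remove part of the drug effect, and no unadjusted model is planned.

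**Working it through.** **1. EAR rates from the plan's own assumptions.** SAP 2.2 gives medians of 58 and 132 minutes, a hazard ratio of 0.44, 30 per arm, 8 dropouts and one-sided 0.05. With exponential times and the 240-minute maximum:

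- placebo: pP = 1 − 2^(−240/58) = 0.943
- drug: pD = 1 − 2^(−240/132) = 0.716

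With 26 evaluable patients per arm, events = 26 × (0.943 + 0.716) = 43.2. Schoenfeld power = Φ(√(43.2/4) × |ln 0.44| − 1.645) = 85.4%, close to the stated 84%. The plan states no power for LAR.

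**2. What the LAR curve counts.** Take a LAR risk after EAR of 0.5 (validation study). The remaining inputs are not in the documents and are varied:

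- r = LAR risk without EAR divided by LAR risk after EAR
- s = share of EAR patients rescued at exit
- u = share of non-EAR patients rescued at exit

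Assume that r, s and u are the same in both arms and that, given EAR status, rescue is unrelated to LAR. Then:

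- true LAR = 0.5 × [p + (1 − p)r]
- counted LAR = 0.5 × [p(1 − s) + (1 − p)r(1 − u)]
- counted gap, placebo minus drug = 0.5 × (pP − pD) × [(1 − s) − r(1 − u)]

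**3. LAR only after EAR (r = 0).** True LAR is 47.2% on placebo and 35.8% on drug: gap 11.3 points, ratio 0.76.

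| Share of EAR patients rescued | Counted placebo | Counted drug | Gap (points) | Ratio |
|---|---|---|---|---|
| 50% | 23.6% | 17.9% | 5.7 | 0.76 |
| 80% | 9.4% | 7.2% | 2.3 | 0.76 |
| 90% | 4.7% | 3.6% | 1.1 | 0.76 |
| 100% | 0 | 0 | 0 | none |

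The ratio is not biased; events and power are lost. In a simulation at 80% rescue (26 per arm, one-sided 5%, 2,000 runs, no drug effect on LAR beyond fewer EARs), power was 21% counting all LARs and 10% with exit rescue competing.

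**4. When the ratio is biased.** Dividing the counted formula by (1 − s) gives a drug/placebo ratio of [pD + (1 − pD)k] / [pP + (1 − pP)k], with k = r(1 − u)/(1 − s). The true ratio has k = r. Because pD < pP, the ratio rises with k. It is therefore shown too high only if r > 0 and u < s.

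With r = 1 (equal LAR risk with and without EAR, true ratio 1.00) and s = 80%:

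| Share of non-EAR patients rescued | Counted placebo | Counted drug | Ratio shown |
|---|---|---|---|
| 0% | 12.3% | 21.3% | 1.74 |
| 40% | 11.1% | 15.7% | 1.41 |
| 80% | 10.0% | 10.0% | 1.00 |

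If every patient is treated at exit (s = u = 100%), both LAR curves are zero.

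**5. The rescue-specific curve.** With all exit rescue at about time 0, this curve is simply the share rescued at exit. At s = 80% and u = 0 that is 0.8 × 94.3% = 75.5% on placebo and 0.8 × 71.6% = 57.3% on drug. SAP 5.4 already tabulates it by arm.

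The FeNO effect cannot be quantified from the documents.

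**The case against.** The strongest reply is that little depends on this analysis. It is optional, the variable is exploratory, and SAP 5.6.3 already plans the sound comparisons: Cox, Kaplan-Meier and Fisher on all LARs, plus time to any asthmatic reaction. The rescue-specific curve is already planned beside the LAR curve. All of this stands, and it keeps the point minor. It does not make the label right.

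A reader might infer that the analysis always works against the drug, or would show more LAR on drug. The documents do not support that. They give neither the LAR rate without EAR nor the rescue share by EAR status. The ratio is unchanged if LAR follows only EAR, and also if both groups are rescued equally often. The trigger includes asthma symptoms short of a 20% fall, and the screening text describes treatment of everyone at exit, so zero rescue among non-EAR patients cannot be presumed. The rescue-specific curve would favour the drug if the drug reduces EAR.

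The 50% LAR risk also transfers imperfectly. It rests on about 10 EAR patients (half of 20) after at most 2 hours of exposure and 6 hours of observation, against 4 hours and 24 hours here.

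One might also fault the LAR fits split by exit rescue and the carry-over covariates. The SAP already presents these as subgroup fits and as exploration, so extra labels there are a reporting preference.

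**Conclusion.** The point holds as a minor one. As written, the optional analysis estimates LAR without exit rescue, because the event treated as competing occurs at about time 0, follows largely from the EAR and leaves LAR possible. It always drops LARs in rescued patients. Where LAR follows only EAR, the true 11.3-point gap shrinks in proportion to the share rescued while the ratio stays at 0.76. Bias of the ratio against the drug is conditional on LAR without EAR and on more frequent rescue after EAR. If everyone is treated at exit, the LAR curve is empty and uninformative. These sizes rest on exponential EAR times at the planning medians, the 50% LAR risk and assumed rescue shares.

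No primary or secondary conclusion is affected, and neither are the Cox model without the carry-over covariate or the Fisher test of all LARs. The FeNO point is clear from the text but unquantified, and it stands separately.

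**What to change.** Delete the exit-rescue competing-risk analysis from SAP 5.6.3, or relabel it 'LAR without exit rescue'. State that the LAR comparison is the planned Cox, Kaplan-Meier and Fisher analysis of all LARs within 24 hours by randomised arm, read together with the rescue tabulation in SAP 5.4.

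For FeNO, make the main model the one without time in the EEU and steroid rescue, and keep the adjusted model as supportive.

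The cost is SAP wording and one extra FeNO fit; no new data are needed. The downside is that any difference between arms in bronchodilator or steroid use, and for FeNO in time spent in the EEU, stays part of the estimated effect and must be read as such.
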